A total of 60 patients will be randomized to four groups consisting of: active PEMF + treatment PIB, sham PEMF + treatment PIB, active PEMF + sham PIB, and sham PEMF + sham PIB. Data collection will include demographics, comorbidities, smoking status, operative factors including number of lymph nodes taken (if any), intraoperative analgesia consumption, type of mastectomy and reconstruction, and postoperative factors such as opioid and narcotic use, time to discharge, nausea/vomiting, pain level using the visual analog scale (VAS) and recovery status using the quality of recovery (QoR) questionnaire. The primary outcome between the groups will be reduction in pain level as assessed by the VAS. Reduction in VAS pain levels will then be compared between all four groups to evaluate the efficacy of PEMF vs. PIB on postoperative pain in mastectomy + tissue expander patients.

LAY ABSTRACT

Chronic pain after mastectomy, or breast tissue removal, is very common with almost half of women experiencing some type of residual pain and even 13% characterizing it as severe. Poor acute postoperative pain control is not only associated with development of chronic pain, but has also been shown to be associated with delayed wound healing. Therefore, optimization of postoperative pain control is paramount not just for patient comfort, but to decrease immediate and long-term postoperative complications. There are two adjunctive modes of perioperative pain control currently in use at Columbia University Medical Center (CUMC). The first mode uses pulsed electromagnetic fields (PEMF) and consists of a noninvasive device placed over dressings around the surgical site. The second is a regional anesthetic and —the pectoral interfascial block (PIB) in which a long-lasting local anesthetic (bupivacaine/ropivacaine) is injected into the surgical dissection area. Both of these techniques for postoperative analgesia have been shown to be effective in different types of breast surgery, but there is no current literature comparing the two modalities in their efficacy in reducing postoperative pain. There is also no current literature in their efficacy in the mastectomy and tissue expander patient population. The proposed trial is a prospective, randomized, controlled, double-blind trial to evaluate the efficacy of these two modalities of postoperative analgesia in patients undergoing mastectomy and tissue expander reconstruction.

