A total of 60 patients will be randomized to four groups consisting of: active PEMF + treatment PIB, sham PEMF + treatment PIB, active PEMF + sham PIB, and sham PEMF + sham PIB. Data collection will include demographics, comorbidities, smoking status, operative factors including number of lymph nodes taken (if any), intraoperative analgesia consumption, type of mastectomy and reconstruction, and postoperative factors such as opioid and narcotic use, nausea/vomiting and pain level using the visual analog scale (VAS) and recovery status using the quality of recovery (QoR) questionnaire. The primary outcome between the groups will be reduction in pain level as quantified by the VAS. Reduction in VAS pain levels will then be compared between all four groups to evaluate the efficacy of PEMF vs. PIB on postoperative pain in patients undergoing mastectomy with tissue expander reconstruction.

RISKS/BENEFITS & MONITORING

POTENTIAL RISKS:

Provide information regarding all risks to participants that are directly related to participation in this protocol,

Version 6

29 June 2021

including any potential for a breach of confidentiality. Risks associated with any of the items described in the Procedures section of this submission should be outlined here if they are not captured in a stand-alone protocol. Risks of procedures that individuals would be exposed to regardless of whether they choose to participate in this research need not be detailed in this section, unless evaluation of those risks is the focus of this research. When applicable, the likelihood of certain risks should be explained and data on risks that have been encountered in past studies should be provided.

PEMF

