The PEMF devices (Ivivi Health Sciences, LLC) are FDA approved for pain and edema relief, and we will be using the devices for their FDA-approved purpose. The pulsed electromagnetic field signal will consist of a 2-msec burst of 27.12-MHz radiofrequency sinusoidal waves repeating at 2 bursts/second [8]. Peak magnetic field was 0.05 G, which induces an average electric field of 4 ± 1 V/m in each target site. The 18-cm coil produces a therapeutically useful signal up to 10 cm above and below the plane of the coil. This will ensure adequate depth of signal penetration (dose) for abdominal/chest wall, subcutaneous, and skin suture line pain. Sham devices will appear identical to and will be used in exactly the same manner as active devices but will produce no electromagnetic field. Both sham and active devices will have indicator lights that blink during pulsed electromagnetic field application. These pulsed electromagnetic field devices do not produce heat.

There have been no reported adverse or side effects in the 40 years that PEMF therapy has been used for recalcitrant fractures, chronic wounds, or post-operative pain relief [7, 9-11]. The primary investigator of the proposed study has extensive experience with these devices and has previously performed double-blind, placebo-controlled trials with breast-reduction patients without any adverse events.

PIB

Bupivacaine/ Ropivacaine is an FDA approved local anesthetic currently used in pectoral interfascial blocks for breast surgery patients. Bupivacaine and Ropivacaine are both long acting local anesthetics with a similar mechanism of action. The anticipated risks with the PIB and sham PIB interventions are those inherent in any injection, which includes bruising, hematoma, and the possibility of intravascular injection. PIB is already actively clinically utilized at CUMC and all patients will be informed of these risks during their informed consent with the option to forego this regional block. Regarding the sham PIB group, intramuscular 0.9% saline injections have been extensively reported in the anesthesia and orthopedic literature [12-14] and are widely regarded as a safe control without appreciable complications or risks to the patient.

POTENTIAL ADVERSE EVENTS RELATED TO THE STUDY

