Potential adverse events related to the study might be local bruising at the injection site, skin reaction to the PEMF device and local anesthetic toxicity which will be determined by clinical assessment. However, local bruising is a minimal concern since these patients often have bruising from the mastectomy. These adverse events will be specifically collected for the study.

POTENTIAL BENEFITS

Provide information regarding any anticipated benefits of participating in this research. There should be a rational description of why such benefits are expected based on current knowledge. If there is unlikely to be direct benefit to participants/subjects, describe benefits to society. Please note that elements of participation such as compensation, access to medical care, receiving study results, etc. are not considered benefits of research participation.

The beneficial effects of PEMF devices on inflammation, pain, healing, etc. have been reported broadly and in a

Version 6

29 June 2021

growing number of fields [11, 15, 16]. Our own studies have demonstrated the dramatic reduction in postoperative pain in patients undergoing TRAM flap reconstruction or breast reduction. As such, patients randomized to the active PEMF device group may benefit from a similar reduction in postoperative pain. Patients in the placebo device group will likely not experience any benefit. Currently, PIB is used widely in CUMC for postoperative anesthesia and patients randomized to PIB may also gain an analgesic benefit [5]. There is no benefit anticipated from the sham PIB.

Despite the beneficial effects of PEMF demonstrated in prior studies, neither PEMF or PIB are widely used analgesic modalities at other institutions. If the proposed study demonstrates benefit for mastectomy and tissue expander reconstruction patients, these results may enable more generalized application of potential beneficial treatments for post-operative pain.

ALTERNATIVES:

If this research involves an intervention that presents greater than minimal risk to participants, describe available alternative interventions and provide data to support their efficacy and/or availability. Note, participants always have the option not to participate in research.

Patients can choose not to participate in this study and will undergo the same surgery with standard postoperative care and pain medication.

DATA STORAGE:

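### Hematoma and intravascular injection are named as risks of the block and sham block, but neither is on the list of adverse events to be collected

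*Combined protocol and SAP*

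**What the plan says.** The protocol has two lists that bear on harm from the injection.

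The PIB paragraph under Potential Risks covers both the active and the sham injection. It describes the anticipated risks as "those inherent in any injection, which includes bruising, hematoma, and the possibility of intravascular injection". It adds that "all patients will be informed of these risks during their informed consent".

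The next section, Potential Adverse Events Related to the Study, lists three events: "Potential adverse events related to the study might be local bruising at the injection site, skin reaction to the PEMF device and local anesthetic toxicity". Toxicity is to be judged by clinical assessment. The section plays down the first event on the ground that "local bruising is a minimal concern since these patients often have bruising from the mastectomy", and it closes with the collection rule: "These adverse events will be specifically collected for the study".

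The other statements of what will be recorded are the data-collection paragraph that precedes Statistical Procedures and the matching paragraphs in the Scientific and Lay Abstracts. Of the possible harms, they mention only nausea/vomiting. They name neither hematoma nor intravascular injection.

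**The concern.** One would expect the risks a protocol names for its intervention to be the ones it records. Here the two lists share a single item. The collection rule refers back to the events just listed, and the protocol nowhere says that adverse events in general will be recorded. A site that followed the stated rule and nothing more would have no place to enter a hematoma at the block site or a recognised intravascular injection.

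This matters most in the sham-PIB patients. Their saline injection is given only because of the trial, and the Potential Benefits section expects no benefit from it. If two of its three named risks are not recorded, a statement that no such events occurred would rest on the absence of a field rather than on observation.

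**Working it through.** The plan gives no figure on this point to reproduce. The check is a comparison of lists.

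| Event | Named injection risk (Potential Risks, PIB) | Collected event (Potential Adverse Events) | Any other data-collection list |
|---|---|---|---|
| Injection-site bruising | yes | yes | no |
| Hematoma | yes | no | no |
| Intravascular injection | yes | no, not by name | no |
| Local anesthetic toxicity | no | yes | no |
| Skin reaction to the device | not an injection risk | yes | no |

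1. Named injection risks: 3. Of these, on the collected list: 1 (bruising). Not on it: 3 − 1 = 2 (hematoma and intravascular injection).

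2. Patients concerned. The Randomization section plans four arms of 15, so 4 × 15 = 60, and every patient is to receive an injection. Sham PIB is given in two arms, 15 + 15 = 30, and treatment PIB in the other two, 15 + 15 = 30.

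3. Indirect capture. The one route by which an intravascular injection could reach the study data is "local anesthetic toxicity which will be determined by clinical assessment". That requires active drug and a clinically apparent effect. It can therefore work only in the 30 treatment-PIB patients, and only for symptomatic events. Saline cannot produce local anesthetic toxicity, so there is no route in the 30 sham-PIB patients.

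4. Hematoma has no equivalent route. Bruising is an adjacent event, but it is listed as bruising, and nothing says that a hematoma is to be entered under it.

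**The case against.** The strongest reply has four parts.

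- **The wording is not exclusive.** The adverse-event sentence is tentative, the data-collection paragraph gives examples, and nothing bars recording other events. This stands against any claim that the trial cannot report these harms, which a reader might infer. The documents show only that collection is not planned. It does not close the gap, because the commitment to collect attaches to the three listed events.
- **Intravascular injection is a mechanism, and its consequence is on the list.** This stands in part, for symptomatic events after active drug. It does not cover saline injections.
- **Bruising is collected.** Correct. The protocol calls it a minor concern but still includes it among the events to be collected, so it should not be read as dropped.
- **Surgical complications are outside the scope.** A reader might infer that leaving out wound infection, delayed healing and expander loss is the same error, particularly as the Lay Abstract says that "optimization of postoperative pain control is paramount not just for patient comfort, but to decrease immediate and long-term postoperative complications". The documents do not support that. The sentence is background on pain control, the wound-healing remark in the Background interprets results from an earlier study, and the three aims concern pain and narcotic use. The protocol does not present these complications as study risks. Non-participants have the same surgery, and the form's own instruction reads: "Risks of procedures that individuals would be exposed to regardless of whether they choose to participate in this research need not be detailed in this" (the risk section). That instruction governs what risks are described, not what data are collected, but it removes any mismatch between the two lists on this point. It does not excuse omitting harms of the trial's own saline injection.

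A reader might also infer that patients are not told about local anesthetic toxicity. That cannot be checked. The consent pages are not in the available text, and the wording of the risk paragraph is not exhaustive. All that can be said is that the paragraph does not name toxicity.

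**Conclusion.** The point holds in this form: two of the three injection risks named in the protocol, hematoma and intravascular injection, are not among the events it commits to collecting, and nothing else in the document picks them up. Hematoma is uncaptured in all 60 planned patients. Intravascular injection is uncaptured in the 30 sham-PIB patients and only partly captured, through toxicity, in the 30 treatment-PIB patients.

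This rests on reading the collection rule as it is written and on the planned allocation. Dropout, or patients who use the stated option to forgo the block, would lower the numbers exposed but would not change the mismatch.

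It is a safety-reporting gap that is cheap to close. It has no bearing on the primary outcome, the sample size or the error rates.

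**What to change.** Reconcile the two lists:

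- In Potential Adverse Events Related to the Study, add hematoma and recognised intravascular injection to the events collected. Record the date and side of each, since surgery may be bilateral.
- In the PIB paragraph under Potential Risks, add local anesthetic toxicity so that the two sections agree.
- State that events will be tabulated for all patients who received an injection, overall and by PIB and PEMF assignment.
- State whether any other adverse events are recorded.

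The cost is a short amendment, a few form fields and a possibly less favourable safety table. The table also has a limit that should be acknowledged: every arm is injected and surgery can itself cause hematoma, so a comparison between arms will not isolate harm from the injection.

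As an option, wound or expander complications seen at the existing 1-week and 3-week visits could be recorded on the same form. Their absence is not an error in the plan, and events after the last visit would still be missed.
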